Idiopathic Parkinson's Disease of moderate severity, Hoehn & Yahr Stage 2-4, age >50, usual (carbohydrate predominant) diet at baseline. A total of 32 PD patients will be recruited predominantly from the Parkinson's Clinic at NIH and local sites given necessity of three visits to facilitate randomization and baseline data acquisition. Recruitment will continue as per power analysis for Timed Up & Go (TUG).

Phase:	1
Description of Sites/Facilities	Enrollment will occur at Screening Visit, NIH Clinical Center Outpatient Clinic 5 (OP5). Admission will occur at NIH Clinical Center Metabolic Unit, 7SW.
Enrolling Participants:	Unit, 7SW.
Description of Study Intervention:	The study intervention is randomization to MCT-KD (ketogenic diet with 80% energy from lipids including Liquigen® (KetoCal) comprising 25% of the daily lipid energy divided twice daily or typical, standard American diet (SAD) x 6 days, followed by 2 weeks ketogenic diet in both groups at home. The proposed diets are isocaloric and have the same ratio of protein (10-15% daily energy) with similar mealtime boluses to limit differences in L-DOPA absorption. Daily activity and exercise plans will be individualized upon admission including use of stationary bike, aiming to maintain baseline levels. Diet with MCT oil will begin on hospital day 2

[figure not shown]
Abbreviated Title: Feasibility and efficacy of ketogenic diet in Parkinson’s Disease

Version Date: 04/19/2021

and be provided to both groups at outpatient day 1 Both diets will be double-blinded (combination of shakes and similar appearing snacks). MCT-KD will feature reduced carbohydrate intake of 5-10% daily energy requirement calculated in the Metabolic Unit. Safety monitoring will be performed by IMM.

Study Duration: 9 months
Participant Duration: 3 weeks

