that certain medications, medication dosages, or DBS status will interact with dietary composition, either ketogenic or standard at standard protein intake. Study raters will remain blinded to diet group, because randomization scheme will be kept only by biostatistician and intervention status will be known otherwise only by nutrition staff, none of whom are involved in study rating. A possible exception is unblinding due to serious adverse event determined by study PI (non-rater) in consultation with safety monitor in which participant continues in the study, in which case data will be demarcated and not included in statistical analysis. Prior to admission, participants will be instructed to complete a log for 1 week of activities and diet at home. Upon admission to the Metabolic Unit and during hospital day 1, they will continue a regular, healthy hospital diet (carbohydrate predominant) and undergo baseline testing in mobility, physiologic and cognitive measures as per Section 3, Objectives and Endpoints). On hospital days 2-7, they will begin one of two diets: diet A, MCT-KD, according to set macronutrient ratios by daily energy: lipid 80% (25% of which is MCT oil), carb 5-10%, protein 10-15%, expected to be better tolerated than traditional NK, vs. diet B, standard American diet, lipid 30-35%, carb 55%, protein 10-15%. The goal is study time series of betaOHB, respiratory quotient, and continuous glucose ketosis measurements with tests of symptomatic impairment, with the hypothesis that nutritional ketosis augments mitochondrial function within hours of keto-induction and provides further benefit over days due to better functional neurotransmitter supply to key motor and cognitive synapses, aside from any long-term disease modification. Added benefits of an inpatient trial include monitored adherence and a look at biomarkers such as respiratory quotient in the metabolic chamber (CO₂:O₂ expected to go down due to diet), as well as easier access to daily repeated testing such as cognitive focused testing on executive function, memory and learning, as well as quantitative motor assessment of bradykinesia (keyboard, 9-hole pegboard), blinded UPDRS, and pain / fatigue assessment by subjective report.

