6.3 MEASURES TO MINIMIZE BIAS: RANDOMIZATION AND BLINDING

As described in Section 9.2 (refer for details), study participants will be randomized after screening visit by study biostatistician. The intervention allocation will be withheld from all study investigators and raters until after the conclusion of all measurements, who will remain blinded to participant allocation for the duration of the study. Refer to Section 9 for details of randomization.

The study nutrition staff will remain unblinded in establishing participant-individualized meal plans. S/he will not disclose any diet details of the admitted participants and will not participate in any of the study measurements. Other investigators will be blinded except due to adverse event or inadvertent event.

Nutrition staff (CC Nutrition Department) will design the blinded diets according to the macronutrient ratios and MCT oil supplementation specified in the study (from calculated daily total energy expenditure by gas exchange on screening visit using Wier formula). Aside from the addition of MCT oil comprising 25% of daily lipids, the diet will be similar to what was used in existing study at the NIH CC Metabolic Unit, NCT03255031 Ketogenic Diet in Alcoholism, as per clinicaltrials.gov description:

Dietary Supplement: Ketogenic Diet (KD) / Standard American (SA) Snacks and Shakes

Abbreviated Title: Tolerability and efficacy of ketogenic diet in Parkinson's Disease

Version Date: 04/19/2021

“Ketogenic Diet (KD) / Standard American (SA) Meals and Shakes: Participants will be randomized to a meal plan of either a ketogenic diet (KD) or standard American (SA) diet at the time they sign the consent. For each meal at breakfast, lunch and dinner, the diets will consist of SA meal (carbohydrate rich) or KD meal depending on treatment randomization... []...To ensure that the diet is double blind...[]...solid snacks are always ketogenic and shakes are either KD or SA.”

From conversation with NIAAA study PI and study nutrition staff, when participants were asked about which diet they believed they received, they usually thought they were receiving ketogenic diet, which appears to support the integrity of the dietary blind.

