Based on the literature of ketogenic diet pilot studies (of 3 months duration or less) that no major adverse event was reported in three ketogenic studies in PD and another three in AD, it is unlikely that a serious adverse event (SAE) related to the intervention will occur. Monitoring will occur by daily clinical assessment (AI / metabolic unit staff) and electrolyte testing.

If there is a major adverse event, including but not limited to: Na <135, K < 3.4, Mag <1.0, HCO₃ < 22, and/or vomiting, study investigators including PI will be immediately made aware by Metabolic Unit staff, discussion will occur with the Independent Medical Monitor within 24 hours as to recommendations for therapy, and participant will be withdrawn from the study and study investigators unblinded to the participant's intervention status unless there is consensus by the IMM and Metabolic Unit staff that ketogenic diet can be continued with other measures taken (e.g. fluid rehydration, anti-nausea medication) or participation continued on a modified / less stringent ketogenic diet.

Despite double-blind design, unblinding may occur inadvertently. The participants will be instructed beforehand to make no mention of their diet, same as Metabolic Unit nurses and dieticians. If however unblinding of study rater(s) does unexpectedly occur, participants will by default remain in the study but be discounted from study power calculation and marked separately for statistical analyses.

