8.4.4 Time Period and Frequency for Event Assessment and Follow-Up

The occurrence of an adverse event (AE) or serious adverse event (SAE) may come to the attention of study personnel during study visits and interviews of a study participant presenting for medical care, or upon review by a study monitor.

Abbreviated Title: Tolerability and efficacy of ketogenic diet in Parkinson's Disease

Version Date: 04/19/2021

All AEs including local and systemic reactions not meeting the criteria for SAEs will be captured on the appropriate case report form (CRF). Information to be collected includes event description, time of onset, clinician's assessment of severity, relationship to study product (assessed only by those with the training and authority to make a diagnosis), and time of resolution/stabilization of the event. All AEs occurring while on study must be documented appropriately regardless of relationship. All AEs will be followed to adequate resolution.

AE will be solicited through daily keto-induction symptom worksheets. Opportunity for unsolicited AE will be provided / encouraged, with instructions for conversation to occur initially with study PI / IMM to maintain blinding of study raters, when AE is not serious and is non-emergent.

Any medical condition that is present at the time that the participant is screened will be considered as baseline and not reported as an AE. However, if the study participant's condition deteriorates at any time during the study, it will be recorded as an AE.

Changes in the severity of an AE will be documented to allow an assessment of the duration of the event at each level of severity to be performed. AEs characterized as intermittent require documentation of onset and duration of each episode.

Study PI will communicate to IMM and record all reportable events with start dates occurring any time after informed consent is obtained until 7 (for non-serious AEs) or 30 days (for SAEs) after the last day of study participation. Study AI will also be involved in evaluation after study completion when non-emergent. Events will be followed for outcome information until resolution or stabilization.

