9.3 POPULATIONS FOR ANALYSES

32 subjects randomized to either ketosis diet or a low fat (standard American) diet

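### Section 6.1.1 excludes data of a randomised participant unblinded for a serious adverse event who continues, without limiting this to rater-assessed values taken after unblinding; 9.3 and 6.3 do not match it

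*Combined protocol and SAP*

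**What the plan says.** Three sections of the combined protocol and SAP bear on who is analysed after unblinding.

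- **6.1.1** makes an exception to rater blinding for a serious adverse event, "in which participant continues in the study, in which case data will be demarcated and not included in statistical analysis". It gives no limit by time or by type of outcome.
- **6.3** covers inadvertent unblinding of a rater: "participants will by default remain in the study but be discounted from study power calculation and marked separately for statistical analyses". For a major adverse event the default is that the "participant will be withdrawn from the study and study investigators unblinded", unless the medical monitor and unit staff agree that participation can go on. No analysis rule is given for those who go on.
- **9.3** gives the analysis population as "32 subjects randomized to either ketosis diet or a low fat (standard American) diet" and names no exception.

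Section 9.4.2 plans an ANCOVA of day-7 TUG, adjusted for age and day-1 TUG. It names no analysis set and no rule for unblinded participants. Intention-to-treat appears only in the abbreviation list.

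**The concern.** An analyst who follows 6.1.1 and one who follows 9.3 would analyse different people. The inclusion rule would then have to be settled after the events, possibly by someone who knows the allocation.

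The trigger comes after randomisation and may be diet-related. Section 8.4.2 uses pancreatitis and kidney stones as examples of serious events. Section 2.3.1 lists both among rare events attributed to ketogenic diet in pediatric epilepsy, and calls them unlikely here. If those removed differ in TUG, the two arms are no longer comparable at day 7. TUG is the secondary outcome, but it sets the sample size.

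The rule has a sound purpose. The associate investigator who times TUG (4.1) may be unblinded when extra care is needed (8.3), and a stopwatch time taken with knowledge of the diet is open to bias. That purpose does not reach a value timed before unblinding, or an outcome that no rater scores. One such outcome is the self-completed exit survey, whose acceptability criterion must be met by all participants (8.2, 9.1).

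**Working it through.** **1. The plan's own figure.** Inputs from 9.2: difference 4.5 s, SD 4 s, two-sided level 0.0492, power 80%. A two-sample t-test (noncentral t) gives 78.4% power with 13 per group and 81.5% with 14, so 14 per group is right. For 10% dropout, 14 / 0.9 = 15.6, rounded up to 16 per group, 32 in all. The stated sample size is reproduced. From 14 v 14, losing 1, 2 or 3 participants from one arm gives 79.9%, 78.1% or 76.0% power.

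**2. What must coincide for 6.1.1 to apply.** There must be an SAE, unblinding because of it, and continuation in the study. Section 6.3 says "it is unlikely that a serious adverse event (SAE) related to the intervention will occur" and withdraws by default after a major adverse event. Section 10.2 stops the study for a major medical event that needs a higher level of care.

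**3. Illustration of bias under the planned analysis.** The documents give no rate of removal and no link between removal and TUG, so these are assumptions. There is no true diet effect, 16 per arm, SD 4 s and level 0.0492. The model is day-7 TUG = b0 + b1·arm + b2·day-1 TUG + b3·age + error. The correlation of day 1 with day 7 is 0.7 or 0.85, and of age with TUG 0.3. From the ketogenic arm, the k participants highest on S = r·Z + √(1 − r²)·e are removed, where Z is standardised day-7 TUG (high = slow) and e is independent noise. There were 200,000 trials per scenario. Ranges cover the two day 1 to day 7 correlations.

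| Removal | Shift in estimate | Two-sided error |
|---|---|---|
| none | 0 | 4.85–4.93% |
| r = 0, k = 1 to 3 | within 0.003 s | 4.8–5.0% |
| r = 0.3, k = 1 | −0.04 to −0.07 s | 4.9–5.0% |
| r = 0.3, k = 2 | −0.07 to −0.13 s | 4.9–5.1% |
| r = 0.5, k = 1 | −0.07 to −0.12 s | 5.0–5.2% |
| r = 0.5, k = 2 | −0.12 to −0.22 s | 5.2–5.5% |
| r = −0.5, k = 2 | +0.12 to +0.22 s | 5.3–5.5% |

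False findings of benefit rise from 2.4–2.5% with no removals to 2.9–3.3% (k = 1) and 3.5–4.0% (k = 2) at r = 0.5. As a share of the 4.5 s target, the r = 0.5 shifts run from 0.066 / 4.5 = 1.5% to 0.219 / 4.5 = 4.9%. Unequal removal alone does no harm (r = 0). It must also be related to TUG.

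**4. The opposite error: keeping a mistimed value.** One value wrong by 1 s among 16 moves the arm mean by 1/16 = 0.0625 s. In simulation (100,000 trials), errors of −1 s and −2 s shifted the estimate by −0.06 s and −0.12 s. Keeping the value is the smaller bias until the timing error passes a break-even:

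- r = 0.5: 0.066 / 0.0625 = 1.1 s to 0.117 / 0.0625 = 1.9 s
- r = 0.3: 0.039 / 0.0625 = 0.6 s to 0.070 / 0.0625 = 1.1 s
- r = 0: any timing error makes exclusion the less biased choice

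So the documents do not settle which treatment of post-unblinding timings is better. For values timed blind the timing error from unblinding is zero, and there is no reason to drop them.

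**The case against.** The strongest reply is that 6.1.1 already means only later data. The sentence is an exception to rater blinding for someone who carries on, and the same section also speaks of demarcating single visits that fall off schedule. That reading is possible, but nothing in the plan states it. The words as written carry no time limit, so the ambiguity stands.

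A second reply is that the case will hardly arise. This is largely right, for the reasons in step 2 of the working. In addition, 2.3.1 says that the rare events it lists were not reported in the adult neurodegenerative studies reviewed, and 5.2 excludes a history of kidney stones.

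A reader might infer two stronger points, which the documents do not support:

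- **A long window after day 7.** SAEs are recorded "until 7 (for non-serious AEs) or 30 days (for SAEs) after the last day of study participation", and the plan provides for "standard American diet (SAD) x 6 days, followed by 2 weeks ketogenic diet in both groups at home", so 14 of the 20 ketogenic-arm diet days (6 + 14) follow day 7. With the "intervention allocation will be withheld from all study investigators and raters until after the conclusion of all measurements", a late event might seem able to erase a day-7 value timed blind. But the rule needs a participant who is still in the study, so events after the last day of participation cannot trigger it. In the home phase both arms are openly on the ketogenic diet, which leaves little reason to open the inpatient allocation. The route exists on the text but is improbable.
- **A serious inflation of error.** An unadjusted t-test with 14 per arm and r = 0.5 gives shifts of about 0.26 s (k = 1) and 0.49 s (k = 2), with error of about 5.5% and 6.4%. The planned analysis is the ANCOVA, for which the smaller figures in the table apply.

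**Conclusion.** The point holds as a conflict of rules with a small expected effect, and it is minor. Section 6.1.1 excludes more than its blinding purpose justifies, 9.3 does not carry the exclusion, and 6.3 leaves a second group undecided. Under the stated assumptions, one or two removals shift the day-7 difference by at most about 0.22 s, and two-sided error is at most about 5.5%. The true size and direction cannot be derived from the documents. They depend on how many are removed, from which arm, and how removal relates to TUG. The sample size of 32 is unaffected.

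What is firm is that values taken before unblinding, and outcomes independent of a rater, should stay in. Whether unblinded timings belong in the main analysis is a judgement that rests on an unknown correlation and an unknown timing error.

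**What to change.** State one rule in 6.1.1, 6.3 and 9.3:

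- All randomised participants are analysed in their assigned arm.
- Values measured before unblinding, and outcomes that do not depend on a rater, are always kept.
- Any exclusion for unblinding, whether after an SAE or inadvertent, covers only rater-assessed measurements made after the rater was unblinded.
- The day-7 TUG ANCOVA is reported with and without those values. The main version is named before allocation is opened, which in practice means before the interim analysis in 9.4.6.
- The date, the reason and the person unblinded are recorded and reported by arm.

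Separately, reconcile the default withdrawal in 6.3 with 7.1, under which stopping the diet is not leaving the study, so that it is clear whose later TUG is collected. No clinical rule is proposed.

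The cost is wording and one extra analysis, with no new outcome measurements. The downside is that a few unblinded timings appear in one of the two versions.

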6.1.2 Dosing and Administration

Dose of the Liquigen® (KetoCal) MCT oil will be calculated individually based on 20% participant daily energy expenditure using the Weir formula. Meals will be combination of solid and blended liquid with care taken for blinding study subjects to ketogenic or standard diet composition.

6.1.2.1 Drug Administration

The MCT oil Liquigen® (KetoCal) will be incorporated into food / beverages for participants in the MCT-KD group by NIH CC Nutrition Department staff, who will not disclose group identity to study raters. Record of food and beverage consumption will be maintained using weight and data entry as per usual practice in nutritional studies at the NIH CC. The purpose of the notification will be to ascertain the

Abbreviated Title: Tolerability and efficacy of ketogenic diet in Parkinson's Disease

Version Date: 04/19/2021

degree of missing data for ketosis intervention; determine if any quality control might be helpful; and see if additional ketosis data are required.

The standard and ketogenic diets will be provided by the Nutrition Department of the Clinical Center. Both diets will be as per provided menu in collaboration with Metabolic Unit staff (study dietician and others). Standard diet will adhere to macronutrient composition lipid 35%, protein 10-15%, carbohydrate 50-55%. Ketogenic diet will incorporate restriction of carbohydrates to reach 80/5-10/10-15 (lipid:carb:protein daily energy) values. The total daily energy will be calculated from respiratory gas exchange in the Metabolic Chamber using the Weir formula (Weir, 1949): Metabolic rate (kcal per day) = 1.44 (3.94 VO₂ + 1.11 VCO₂). Both ketogenic and standard diets will be eucaloric, providing recommended daily calories.

6.2 PREPARATION/HANDLING/STORAGE/ACCOUNTABILITY

N.A.

6.2.1 Acquisition and Accountability

The Liquigen® (KetoCal)MCT oil is carried by the Clinical Center Nutrition Department and will be made available for the diet preparation.

6.2.2 Formulation, Appearance, Packaging, and Labeling

As per Liquigen® (KetoCal) Product Bulletin
(URL: < <https://shop.myketocal.com/product/liquigen>>):

- **Ingredients:** Refined coconut and/or palm kernel oil, water, citric acid esters of mono and diglycerides (emulsifier), mono and diglycerides (emulsifier), citric acid.
 - Unflavored For oral or enteral use
 - kcal/mL: 4.5
 - Caloric Distribution (% of kcal)
 - Protein: 0%
 - Carbohydrate: 0%
 - Fat: 100%

Recommended Usage:

- **Oral Administration:** It may be mixed into beverages and foods.

Abbreviated Title: Tolerability and efficacy of ketogenic diet in Parkinson's Disease

Version Date: 04/19/2021

6.2.3 Product Storage and Stability

This product will be stored in the original plastic 250 mL bottle.

6.2.4 Preparation

MCT Oil® (Nestle) MCT oil will be mixed by Nutrition Department Dietary services at the Clinical Center. It will be added to other ketogenic foods prepared as per the study menu.

Outpatient ketogenic diet

According to participant decision after discussion during the screening and admission, willing participants are instructed to continue ketogenic diet as defined by CC nutrition staff customized from provided meal plans provided to each participant.

Diet tracking with information on macronutrient and micronutrient composition will occur via unscheduled phone calls by study dietitians conducting 24 hour food recall, input to NDSR04 software.

6.3 MEASURES TO MINIMIZE BIAS: RANDOMIZATION AND BLINDING

As described in Section 9.2 (refer for details), study participants will be randomized after screening visit by study biostatistician. The intervention allocation will be withheld from all study investigators and raters until after the conclusion of all measurements, who will remain blinded to participant allocation for the duration of the study. Refer to Section 9 for details of randomization.

The study nutrition staff will remain unblinded in establishing participant-individualized meal plans. S/he will not disclose any diet details of the admitted participants and will not participate in any of the study measurements. Other investigators will be blinded except due to adverse event or inadvertent event.

Nutrition staff (CC Nutrition Department) will design the blinded diets according to the macronutrient ratios and MCT oil supplementation specified in the study (from calculated daily total energy expenditure by gas exchange on screening visit using Wier formula). Aside from the addition of MCT oil comprising 25% of daily lipids, the diet will be similar to what was used in existing study at the NIH CC Metabolic Unit, NCT03255031 Ketogenic Diet in Alcoholism, as per clinicaltrials.gov description:

Dietary Supplement: Ketogenic Diet (KD) / Standard American (SA) Snacks and Shakes

Abbreviated Title: Tolerability and efficacy of ketogenic diet in Parkinson's Disease

Version Date: 04/19/2021

“Ketogenic Diet (KD) / Standard American (SA) Meals and Shakes: Participants will be randomized to a meal plan of either a ketogenic diet (KD) or standard American (SA) diet at the time they sign the consent. For each meal at breakfast, lunch and dinner, the diets will consist of SA meal (carbohydrate rich) or KD meal depending on treatment randomization... []...To ensure that the diet is double blind...[]...solid snacks are always ketogenic and shakes are either KD or SA.”

From conversation with NIAAA study PI and study nutrition staff, when participants were asked about which diet they believed they received, they usually thought they were receiving ketogenic diet, which appears to support the integrity of the dietary blind.

Based on the literature of ketogenic diet pilot studies (of 3 months duration or less) that no major adverse event was reported in three ketogenic studies in PD and another three in AD, it is unlikely that a serious adverse event (SAE) related to the intervention will occur. Monitoring will occur by daily clinical assessment (AI / metabolic unit staff) and electrolyte testing.

If there is a major adverse event, including but not limited to: Na <135, K < 3.4, Mag <1.0, HCO₃ < 22, and/or vomiting, study investigators including PI will be immediately made aware by Metabolic Unit staff, discussion will occur with the Independent Medical Monitor within 24 hours as to recommendations for therapy, and participant will be withdrawn from the study and study investigators unblinded to the participant's intervention status unless there is consensus by the IMM and Metabolic Unit staff that ketogenic diet can be continued with other measures taken (e.g. fluid rehydration, anti-nausea medication) or participation continued on a modified / less stringent ketogenic diet.

Despite double-blind design, unblinding may occur inadvertently. The participants will be instructed beforehand to make no mention of their diet, same as Metabolic Unit nurses and dieticians. If however unblinding of study rater(s) does unexpectedly occur, participants will by default remain in the study but be discounted from study power calculation and marked separately for statistical analyses.

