7. STUDY INTERVENTION DISCONTINUATION AND PARTICIPANT DISCONTINUATION/WITHDRAWAL

7.1 DISCONTINUATION OF STUDY INTERVENTION

Discontinuation from dietary intervention does not mean discontinuation from the study, and remaining study procedures should be completed as indicated by the study protocol. If a clinically significant finding is identified (including, but not limited to changes from baseline) after enrollment, the investigator or qualified designee will determine if any change in participant management is needed. Any new clinically relevant finding will be reported as an adverse event (AE).

Holding criteria: Study intervention(Liquigen® (KetoCal)) and ketogenic diet) will be withheld if clinically significant cardiac arrhythmia is detected on baseline ECG (please refer to Clinical Evaluations Section 8.2 for details).

The data to be collected at the time of study intervention discontinuation will include the following:

- diet menu and record
- patient interview with worksheets and symptoms
- height, weight, vital signs including orthostatic (supine x 10min, immediately and 3min after standing); physical examination with focused neurologic examination

Stopping criteria:

- 1.) Patient request
- 2.) If any investigator judges that continuing the procedure would be detrimental to the patient's health and well-being or that clinically meaningful data is not being obtained for other reasons.

An investigator may discontinue or withdraw a participant from the study for the following reasons:

- Completion of study intervention
- Disease progression which requires discontinuation of the study intervention
- If any clinical adverse event (AE), laboratory abnormality, or other medical condition or situation occurs such that continued participation in the study would not be in the best interest of the participant
- Investigator discretion
- Positive pregnancy test
- Participant unable to receive study intervention for more than 1 day

Abbreviated Title: Tolerability and efficacy of ketogenic diet in Parkinson's Disease

Version Date: 04/19/2021

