7.2 PARTICIPANT DISCONTINUATION/WITHDRAWAL FROM THE STUDY

Prior to removal from study, effort must be made to contact all study participants via telephone to determine safety regarding the intervention approximately 2-4 weeks following the last dose of study therapy.

Participants are free to withdraw from participation in the study at any time upon request.

An investigator may discontinue or withdraw a participant from the study for the following reasons:

- Significant study intervention non-compliance
- If the participant meets an exclusion criterion (newly developed) that precludes further study participation
- Subject has completed the study follow-up period

- Screen Failure

The reason for participant discontinuation or withdrawal from the study will be recorded on the Case Report Form (CRF). Subjects who sign the informed consent form and are randomized but do not receive the study intervention may be replaced. Subjects who sign the informed consent form, and are randomized and receive the study intervention, and subsequently withdraw, or are withdrawn or discontinued from the study, will not be replaced.

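### Section 6.3 makes leaving the study, not just the diet, the default after vomiting or listed laboratory values, in conflict with Sections 7.1 and 2.3.1; the likely effect on day-7 TUG is small and the repair is cheap

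*Combined protocol and SAP*

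**What the plan says.** Section 6.3 names sodium <135, potassium <3.4, magnesium <1.0, bicarbonate <22 and vomiting as examples of a major adverse event. It attaches no severity grade, repeat test or persistence condition. The independent medical monitor (IMM) is consulted within 24 hours and the "participant will be withdrawn from the study and study investigators unblinded", "unless there is consensus by the IMM and Metabolic Unit staff that ketogenic diet can be continued with other measures taken", or participation continues on a less stringent ketogenic diet.

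Other sections handle the same situation differently:

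- **Section 7.1:** "Discontinuation from dietary intervention does not mean discontinuation from the study, and remaining study procedures should be completed". Withdrawal for an adverse event or laboratory abnormality is something an investigator may do, when "continued participation in the study would not be in the best interest of the participant". A further discretionary reason for withdrawal is "Participant unable to receive study intervention for more than 1 day".
- **Section 2.3.1:** acidosis, vomiting and electrolyte derangement may lead to removal, and only if severe.
- **Section 8.2.3:** an abnormal electrolyte result is repeated and treated, with reduction of the lipid or MCT share of the diet as one option. Removal is not mentioned.
- **Section 8.3:** the diets will not be modified.
- **Section 7.2:** treated participants who "subsequently withdraw, or are withdrawn or discontinued from the study, will not be replaced".

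**The concern.** Staff facing one episode of vomiting, or one bicarbonate value of 21, find different instructions in different sections. Read literally, Section 6.3 takes the participant out of the study unless there is positive agreement to carry on with a ketogenic diet. It has no middle course in which the diet stops and the participant stays for testing, although Section 7.1 prescribes exactly that. The exception is also worded only for a ketogenic diet, so how it applies to a triggered SAD participant is not stated.

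Two things are at stake. Section 8.4.3.1 lists electrolyte depletion, metabolic acidosis and vomiting as ketogenic-diet risks, and on days 2 to 7 only the MCT-KD arm receives that diet. A withdrawal default tied to those events could therefore remove more of that arm before the day-7 TUG, the comparison on which the trial is sized. Section 9 gives no missing-data method for it. In addition, because withdrawn participants are not replaced, a treatable finding would count against the retention criterion of more than 80%, one of the conditions that must all be met for the primary feasibility outcome.

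**Working it through.** **1. The texts side by side**

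| Question | 6.3 | 7.1 | 2.3.1 | 8.2.3 / 8.3 |
|---|---|---|---|---|
| Is withdrawal automatic? | Yes, unless consensus | No, discretionary | No, possible | 8.2.3: not mentioned |
| Severity condition? | None | Best interest of participant | Severe only | 8.2.3: attribution or medical significance |
| Stop diet, stay in study? | Not offered | Yes | Silent | Silent |
| Modify diet? | Allowed | Silent | Silent | 8.2.3 allows, 8.3 bars |

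The discretionary clause in 7.1 on more than 1 day without the intervention partly undoes that section's own rule: a participant whose diet is stopped early in the admission will meet it before day 7.

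**2. The plan's sample size (Section 9.2)**

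Inputs: difference 4.5 s, SD 4 s, two-sided alpha 0.0492, 80% power. Noncentral t power with noncentrality 4.5 / (4 × √(1/n1 + 1/n2)) gives 0.784 at 13 per group and 0.815 at 14 per group. So 14 per group is the smallest size that reaches 80%, and 28 / 0.9 = 31.1, taken to 32. The plan's figures reproduce.

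**3. Retention margin**

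0.80 × 32 = 25.6. 26/32 = 81.25% passes and 25/32 = 78.1% fails, so at most 32 − 26 = 6 losses are allowed.

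- With no other losses, 6 + 1 = 7 withdrawals under 6.3 fail the criterion (7/32 = 21.9%).
- If ordinary dropout of 10% takes 3 (0.10 × 32 = 3.2), then 6 − 3 + 1 = 4 fail it (4/32 = 12.5%, or 4/16 = 25% if all are in MCT-KD). If the planned 10% already includes these events, this case counts them twice.

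The documents give no trigger or withdrawal rate. For assumed MCT-KD withdrawal probabilities, after the exception, of 0.05, 0.10 and 0.20, with X binomial on 16:

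- P(X ≥ 4) = 0.007, 0.068, 0.402
- P(X ≥ 7) = below 0.0001, 0.0005, 0.027

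**4. Power for day-7 TUG (same formula)**

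| MCT-KD / SAD analysed | Power |
|---|---|
| 16 / 16 | 0.867 |
| 14 / 16 | 0.841 |
| 12 / 16 | 0.807 |
| 14 / 14 | 0.815 |
| 12 / 14 | 0.781 |
| 11 / 14 | 0.760 |

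**5. Possible bias, for illustration only**

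Assume that k of 16 in MCT-KD are lost, and that they differ from those who stay by one SD of day-7 TUG after adjustment for day-1 TUG. The day-1/day-7 correlation r is assumed to be 0.7 to 0.9. The arm mean then shifts by (k/16) × 4 × √(1 − r²).

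- r = 0.7: the residual SD is 2.86 s; shifts are 0.18, 0.36 and 0.54 s for k = 1, 2, 3.
- r = 0.9: the residual SD is 1.74 s; shifts are 0.11, 0.22 and 0.33 s.
- No adjustment: 0.25, 0.50 and 0.75 s.

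The design difference is 4.5 s.

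**The case against.** The default is subject to prompt review, and the exception names fluids and anti-nausea medication, which are treatments for the mild findings at issue. Section 8.2.3 and the footnote to the Schedule of Activities (Section 1.3) call for electrolytes to be repeated on days 6 and 7 after an earlier abnormality. That presupposes that such participants are still in the study. Section 7.1 itself allows withdrawal for a laboratory abnormality, and 2.3.1 is a risk narrative, not an operating rule. The nearest attrition figure in the documents is 9% attributed to diet in an eight-week Parkinson's trial (Table 1, Section 2.1). It is not a trigger rate, but 0.09 × 16 = 1.4 participants would shift the adjusted mean by only 0.09 × 1.74 = 0.16 s to 0.09 × 2.86 = 0.26 s.

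Most of this stands, and it limits the size of the point. It does not remove the conflict. The exception still needs positive agreement, and it still covers only continuing a ketogenic diet.

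Three stronger readings are tempting, and the documents do not support them.

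- **Day-7 TUG is missing because the 7.1 list omits it.** The passage beginning "The data to be collected at the time of study intervention discontinuation will include the following" concerns that moment only. The same section asks for the remaining procedures, and TUG is scheduled daily.
- **Unblinding under 6.3 biases later ratings.** One condition governs both withdrawal and unblinding. A participant unblinded by this rule has left the study and has no later rating. One who stays is, on the natural reading, not unblinded. Accidental rater unblinding has its own rule: "If however unblinding of study rater(s) does unexpectedly occur, participants will by default remain in the study", with the data marked separately.
- **The exclusion of data after unblinding for a serious event (Section 6.1.1) should be reversed in the main analysis.** With testing done mainly by one rater (Section 4.1), that exclusion is a defensible choice. Including those data is at most a sensitivity analysis.

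**Conclusion.** The point holds as a wording conflict with a plausible but modest consequence. It is certain that Section 6.3 prescribes withdrawal from the study where 7.1 prescribes staying and 2.3.1 requires severity, and that the sections disagree on diet modification. It is plausible, not certain, that losses would fall more on MCT-KD: the triggers apply to both arms, and the exception is silent on SAD.

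How often withdrawal would follow cannot be derived from the plan. On the assumptions shown, the retention criterion fails at four to seven such withdrawals, depending on other losses. Losing four MCT-KD participants from a full trial leaves TUG power at 0.81, and the illustrative bias stays near half a second or less for up to three losses. A reader might infer that the day-7 comparison is seriously threatened; these figures do not show that.

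A stop that the IMM and unit staff agree cannot be managed is a genuine feasibility failure and should count as one. The fault is a default that also covers treatable findings. Correcting it is a cheap improvement worth making.

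**What to change.** - **6.3:** for both diets, make the default that the diet is treated around, modified or stopped as the IMM advises, while the participant stays for the scheduled day-7 and week-3 assessments if willing and safe. Unblind only non-rating clinicians who need to know, in line with 8.4.3.1 and 8.4.4, and word 8.3 to match. The clinical thresholds remain with the sponsor and the IMM.
- **7.1:** let the clause on more than 1 day without the intervention lead to stopping the diet, not to study withdrawal.
- **6.3, 8.2.3 and 8.3:** state one rule on whether the diet may be modified.
- **9.3 or 9.4:** add a sentence that these participants are analysed in their randomised arm.
- **Feasibility composite:** count a participant who stops the diet as not completing the diet, so that the 80% criterion does not become easier to pass, and report study follow-up separately.

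The cost is amendment text. No visits are added, because the day-7 and week-3 assessments are already scheduled. The downside is some dilution of the diet contrast, since some analysed participants will have stopped their assigned diet.
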